GENOTROPIN (5 mg) is dispensed in a two-chamber cartridge. The front chamber contains recombinant somatropin (5.8 mg), glycine (2.2 mg), mannitol (1.8 mg), sodium dihydrogen phosphate anhydrous (0.32 mg), and disodium phosphate anhydrous (0.31 mg); the rear chamber contains 0.3% m-Cresol (as a preservative) and mannitol (45 mg) in 1.14 mL water for injection. The reconstituted concentration is 5 mg/ml. GENOTROPIN will be administered utilizing the GENOTROPIN Pen 5 (manufactured by Pfizer, Inc). The GENOTROPIN Pen 5 is a reusable multi-dose pen that the two-chambered cartridge is inserted into. Once the cartridge is inserted into the pen, the two-chambers are mixed. A 31 gauge, ½ inch needle is attached to the pen for administration. The pen can then be dialed on the digital display to the correct dose and administered by the user. The needle is then carefully removed and disposed in a sharps medical waste container provided by the study team. Once the cartridge is empty, a new cartridge can be inserted into the pen, a 5 mg cartridge will last 1 – 2 weeks depending on the dose used. The GENOTROPIN Pen 5 is designed to be easily used, as most GH replacement is for pediatric use. Subjects will undergo a familiarization session with the study team to learn how to load the GENOTROPIN5 cartridges into the GENOTROPIN Pen 5 device, how to dial their dose, and how to administer injections. They will also be given a guide and the web address (<http://www.genotropin.com/genotropin-helpful-tools>) of a video prepared by the makers of GENOTROPIN to take home for reference.

In this study, single injections containing 0.4 mg of GENOTROPIN will be administered to mTBI and PASC subjects on a daily basis until the IGF-1 safety check at month 1. If the IGF-1 value is less than 400 ng/mL, the subject will be directed to increase the dose to 0.6 mg per day for the remainder of the study. 0.6 mg per day is the standard dose given in our TBI research studies. We have treated approximately 60 TBI research subjects over approximately 14 years at this dose without incident. [name] also has approximately 100 patients in his clinic being treated at 0.6

mg per day. At this dose of GH replacement, there is no evidence of insulin resistance and as long as the IGF-1 remains at or below 400 ng/mL, there is minimal risk of carpal tunnel syndrome.

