- **Screening Blood Labs.** Subjects will have the following labs drawn for screening. Approximately 20 ml of blood will be drawn for screening labs listed below. The labs will be sent to the UTMB clinical laboratory for analysis and entered into the subjects UTMB medical chart. Labs may be omitted if subject has recent (within 6 months) labs on file.

- Complete blood count with differential (CBC w/ diff)
- Comprehensive metabolic panel (CMP)
- Lipid Panel
- Hepatitis B surface antigen
- Hepatitis C virus antibody
- HIV screen
- Thyroid-stimulating hormone (TSH)
- Prolactin
- Testosterone Total (men only)
- Insulin-like Growth Factor 1 (IGF-1)

- Cortisol
- Glucagon stimulation test. Subjects will have a glucagon stimulation test. After the IV is placed, 3.5 ml of blood will be collected for the baseline (time: 0 minutes) to test for levels of human growth hormone. 1 mg glucagon (for subjects over 90 kg, 1.5 mg glucagon) will be injected IM in the deltoid muscle of the subject. Additional blood samples (3.5 mL) will be collected to test for levels of human growth hormone at time points: 90 minutes, 120 minutes, 150 minutes, and 180 minutes. All blood samples will be sent to UTMB clinical laboratory for analysis and entered into subjects UTMB medical chart. GST may be omitted if subject has recent (within 6 months) GST on file.
- History and Physical. Subjects will undergo a medical history and physical examination by a study nurse or physician. Recent (within 3 months) clinical history and physical may be used in place.

Screening procedures for household controls (Arm 1) and healthy controls (Arm 2): All control subjects consenting to be screened will undergo the following procedures. Subjects will be fasted for at least 10 hours prior to blood work. Screenings will take place at the UTMB Clinical Research Center (CRC).

- Vital signs. Vital signs will be collected at screening. This will include height, weight, blood pressure, pulse, respirations, and temperature. Vital signs will be recorded on the screening CRF.
- Urine Pregnancy Test. Urine will be collected from female subjects for a urine pregnancy test to be performed at the UTMB CRC as POCT. Women who are post-menopausal will be exempt from this test.
- Phlebotomy. Household control subjects will have blood taken using a 21-gauge butterfly needle.

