- Screening Blood Labs. Household controls will have the following labs drawn for screening. Approximately 20 ml of blood will be taken for screening labs listed below. The labs will be sent to the UTMB clinical laboratory for analysis and will be entered into subjects UTMB medical chart:
 - Complete blood count with differential (CBC w/ diff)
 - Comprehensive metabolic panel (CMP)
 - Lipid Panel
 - Thyroid-stimulating hormone (TSH)
 - Hepatitis B surface antigen
 - Hepatitis C virus antibody
 - HIV screen
- History and Physical. Household control subjects will undergo a medical history and physical examination by a study nurse or physician.

Study Procedures for mTBI subjects (Arm 1 & 2) / PASC subjects (Arm 3):

mTBI and PASC subjects will complete all procedures listed below. Differences in procedures between Arm 1, Arm 2 and Arm 3 will be noted.

- Vital signs. Vital signs will be collected at all study visits. This will include height, weight, blood pressure, pulse, respirations, and temperature. Vital signs will be recorded on the appropriate study visit CRF.
- Blood draw. Subjects will have blood drawn at the baseline (month 0), safety check (month 1), post-study (month 6) and final study (month 12 – Arm 3 PASC only) visits. Blood will be drawn using a butterfly needle from a peripheral vein in the arm.

- Baseline Visit (Month 0):

Up to 15 ml of blood (1-serum separator top (5ml); 1-lithium heparin (6ml); 1-K-EDTA (4ml)) will be collected from fasted (at least 10 hours) subjects for analysis of hormones, amino acids and metabolites. In addition, up to 13ml of blood (1-serum separator top (5ml); 1-lithium heparin (6ml)) will be collected after a standardized meal for the analysis of amino acids.

- Safety Check Visit (Month 1):

Approximately 3.5 ml of blood for Insulin-like growth factor 1 (IGF-1) will be collected. Blood will be sent to UTMB clinical laboratory for analysis and documented in the subject's UTMB medical chart.

- Post Visit (Month 6):

Up to 15 ml of blood (1-serum separator top (5ml); 1-lithium heparin (6ml); 1-K-EDTA (4ml)) will be collected from fasted (at least 10 hours) subjects for analysis of hormones, amino acids and metabolites. In addition, up to 13ml of blood (1-serum separator top (5ml); 1-lithium heparin (6ml)) will be collected after a standardized meal for the analysis of amino acids.

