2. Significant heart, liver, kidney, blood or respiratory disease.
3. History of chest pain or coronary heart disease.
4. Uncontrolled Diabetes mellitus.
5. Any history of a recently (12 months) diagnosed cancer other than a skin cancer (excluding melanoma).
6. Current alcohol or drug abuse.
7. Premorbid history of psychiatric disorder.
8. Premorbid history of head trauma.
9. Pregnancy or become pregnant during the trial.
10. Subjects who are deficient in cortisol or thyroid at screening will be excluded until hormone abnormalities have been corrected.
11. Subjects with chronic pain who are being managed with narcotics will be excluded as the effects of central nervous system depressants may interfere with study test results.
12. Subjects with a history of inflammatory bowel disease, Celiac disease or active diverticular disease.
13. Subjects with MRI incompatible devices.
14. Subjects with severe claustrophobia.
15. Other medical condition or medication administration deemed exclusionary by the study investigators.

Household Control Inclusion criteria

1. Ages 18 and up.
2. Lives in same household as paired mTBI subject that meets inclusion/exclusion criteria.
3. Participant is willing and able to give informed consent for participation in the study.

Household Control Exclusion criteria

1. Significant heart, liver, kidney, blood or respiratory disease.
2. Uncontrolled Diabetes mellitus.
3. Any history of a recently (12 months) diagnosed cancer other than a skin cancer (excluding melanoma).
4. Current alcohol or drug abuse.
5. Premorbid history of psychiatric disorder.
6. Premorbid history of head trauma.

7. Pregnancy or become pregnant during the trial.
8. Subjects who are deficient in thyroid at screening will be excluded until thyroid hormone is replaced.
9. Subjects with a history of inflammatory bowel disease, Celiac disease or active diverticular disease.
10. Other medical condition or medication administration deemed exclusionary by the study investigators.

ARM 2:

mTBI Inclusion criteria

1. Male or female with a diagnosis of mild TBI.
2. At least 6-month post-injury.
3. Ages 18 to 70 years.
4. Participant is willing and able to give informed consent for participation in the study.

mTBI Exclusion criteria

1. Unable to walk unassisted.
2. Significant heart, liver, kidney, blood or respiratory disease.
3. History of chest pain or coronary heart disease.
4. Uncontrolled Diabetes mellitus.

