Glucagon Stimulation Testing. The known side effects of the glucagon stimulation test are headache and nausea and possible vomiting.

Electrocardiogram (EKG). This is a non-invasive, painless test. There is a risk of irritation or a rash on the skin from the electrodes.

DEXA scan. The measurement of lean and fat mass by DEXA involves a brief exposure (~15 min) to a low dose of radiation (~ 0.05 mrem/whole body scan), calculated to be approximately equal to a 2 h airplane flight per scan. Otherwise, there are no known risks of measuring body composition.

Indirect calorimetry. There are no known risks involved with these measurements.

Magnetic Resonance Imaging (MRI) (Arm 1 only). As MRI is a procedure that does not involve radiation and is non-invasive, the main risks are accidental injury resulting from the presence of metal objects on one's clothes or person (e.g. jewelry, piercings, implants, pacemakers, some types of tattoos, IUDs). In addition, some individuals may experience claustrophobia due to the confined space within the scanner.

Cognitive Testing. There are no known risks involved with this testing.

Fecal Sampling. There is no known risk of this procedure.

Nasal Swab. Risks include momentary pain and a chance for minor bleeding from the nose similar to the risks associated with nasopharyngeal SARS-CoV-2 testing.

Performance testing and 6-minute walk. The exercise tests may cause muscle soreness, cramps, dizziness, and possibly irregular heartbeats. The risks of the 6-minute walk include falling, elevated heart rate and elevated blood pressure. All subjects will be accompanied by a trained staff member.

Questionnaires. There is no known risk to completing the questionnaires listed in this study.

Recombinant Human Growth Hormone (rhGH). The potential risks of taking growth hormone include weight gain, joint pain, and increased blood glucose. In addition, Carpal Tunnel Syndrome, a condition characterized by numbness or pain in the wrists and fingers, has been associated with growth hormone therapy. These effects are modifiable with dose adjustment and are unlikely due to the relatively brief period of time that patients will be receiving growth hormone during the course of the study. An IGF-1 lab will be drawn at the 1-month time point. If the IGF-1 value is over 400 ng/ml, the dose of GH will not be increased.

Confidentiality. Divulgation of personal sensitive data is a general risk of clinical investigations involving human subjects.

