Magnetic Resonance Imaging. Subjects will be screened for the presence of implanted medical devices, embedded metal or other material for which MRI is contraindicated according to standard UTMB safety guidelines. To protect against loud noises, participants will wear foam earplugs and / or headphones to reduce the loud noises made by the scanner. To reduce claustrophobia, subjects will be able to talk to investigators throughout the study via intercom, and will be able let us know right away if they want to stop the study and get out of the scanner.

Fecal Sampling. There are no known risks of this procedure.

Nasal Swab. Care will be taken to minimize pain and/or bleeding.

Performance testing and 6-minute walk. Risk of muscle soreness or cramps can be reduced or avoided with an adequate warm-up. The subjects will be accompanied by a qualified staff member at all times.

Questionnaires. There are no known risks of this procedure.

Recombinant Human Growth Hormone Administration. The potential risks of taking growth hormone (weight gain, increased blood glucose, joint pain, and Carpal Tunnel Syndrome), will be described in the consent form. These effects are unlikely due to the relatively brief period of time that subjects will be receiving growth hormone during the course of the 6 or 9-month treatment period. An IGF-1 lab will be drawn at the 1-month time point. If the IGF-1 value is over 400ng/ml, the dose of GH will not be increased.

Confidentiality. Only the investigators, the study personnel, and the Medical Records department of the UTMB Hospital will have access to the subjects' personal information. All data containing the name of the patients will be locked in the PI office. To preserve confidentiality, immediately after enrollment each subject will be assigned a code by which each research sample will be identified for further analysis, thus avoiding identification by non-qualified individuals.

C. Potential Benefits of the Proposed Research to the Subjects and Others

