- c. Potential subjects will be informed of all procedures involved in the study. If screening reveals any clinical abnormalities, subjects will be advised, by either a study team physician or nurse practitioner, to consult his/her primary physician. If the subject agrees to participate, written consent will be obtained in the presence of one of the following: the Principal Investigator, Co-Investigator, or Study Coordinator. There will always be at least one qualified member of the research team or one CRC nurse with the subject during the study protocol.

Plan for Data Management:

- a. All the study data will be collected by the research team and recorded on case report forms. To preserve confidentiality, immediately after enrollment each subject will be assigned a code by which each research sample will be identified for further analysis to avoid identification by non-qualified individuals. [name], the Principal Investigator, is the individual responsible for storage of data. Recognizable personal subject information will be stored in [name] laboratory in a locked cabinet.
- b. Data will be reviewed on a weekly basis by the PIs and the research team.
- c. The conditions that would necessitate early termination of the study include non-compliance with study medication dosing.
- d. The PI with the aid of the Co-Investigators and the Study Coordinator will perform aggregate analysis of data and adverse events.

Persons Responsible for Data Monitoring:

The ultimate responsibility for data and safety monitoring, and submitting reports of unanticipated problems, adverse events, protocol deviations and protocol violations rests with the Principal Investigator, [name]. Every effort will be undertaken to monitor and minimize the risks

to subjects. Prior to obtaining informed consent, subjects will be encouraged to thoroughly read the informed consent form and ask questions regarding the outlined procedures and risks. To ensure ongoing protection of study subjects all procedures will be performed under the supervision of [name]., or a physician willing to provide backup medical coverage. All study physicians will be familiar with the study protocol.

Reporting Unanticipated Problems, Adverse Events, Protocol Deviations and Protocol Violations:

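### Raised blood glucose is a named rhGH risk, but no on-drug glucose is scheduled until month 6, when mTBI treatment ends

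*Combined protocol and SAP*

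**What the plan says.** **Risk.** Under Potential Risks, the rhGH paragraph states: "The potential risks of taking growth hormone include weight gain, joint pain, and increased blood glucose". It adds that these effects can be managed by adjusting the dose and are unlikely because treatment is short. Adequacy of Protection Against Risks repeats the list ("The potential risks of taking growth hormone (weight gain, increased blood glucose, joint pain, and Carpal Tunnel Syndrome), will be described in the consent form") and names one laboratory test, IGF-1 at month 1.

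**Eligibility.** The diabetes exclusion for mTBI subjects in Arms 1 and 2 is "Uncontrolled Diabetes mellitus"; Arm 3 has the same criterion. Controlled diabetes is not named. Each arm also has a discretionary item: "Other medical condition or medication administration deemed exclusionary by the study investigators".

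**Blood schedule.** Study Procedures, Blood draw, lists draws for treated subjects at months 0, 1 and 6, and at month 12 for PASC only. For the month 1 safety check it says: "Approximately 3.5 ml of blood for Insulin-like growth factor 1 (IGF-1) will be collected". The comprehensive metabolic panel (CMP) is listed at screening, at month 6 and, for PASC, at month 12. For PASC screening, "Labs may be omitted if subject has recent (within 6 months) labs on file". Fasted blood at month 0 and month 6 also goes to hormones, amino acids and metabolites that are not specified.

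**Dose and duration.** The step from 0.4 to 0.6 mg/day after month 1 depends on IGF-1 alone. Treatment lasts 6 months for mTBI and 9 months for PASC, and an mTBI subject with a new TBI receives 6 further months. On glucose metabolism, Therapeutic Intervention says: "At this dose of GH replacement, there is no evidence of insulin resistance".

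**Monitoring.** The Data Safety and Monitoring Plan says the investigators will follow subjects' laboratory values throughout the study.

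**The concern.** The protocol's own answer to raised glucose is that it is unlikely and can be dealt with through the dose. The second half of that answer needs a glucose value obtained on drug, and the schedule supplies none before the month 1 dose step or in the 5 months after it. The IGF-1 check does not fill the gap: Therapeutic Intervention links the 400 ng/mL limit to carpal tunnel syndrome, not to glucose.

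At stake is a laboratory change without symptoms in any of the 75 treated subjects (25 + 25 + 25), some of whom may have controlled diabetes. For mTBI it would be seen only once treatment was over. There is a reporting cost as well: outside any unscheduled testing, each treated subject contributes one on-drug chemistry panel, so the trial can say little about when a rise began.

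**Working it through.** **Step 1. Could an unlisted panel sit at month 1?** The stated blood totals allow a check. Inputs come from the Screening Procedures and Blood draw sections.

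- Screening: 20 + 5 × 3.5 (glucagon test) = 37.5 ml
- Month 0: 15 + 13 = 28 ml
- Month 1: 3.5 ml
- Month 6: 15 + 13 + 20 = 48 ml
- mTBI total: 37.5 + 28 + 3.5 + 48 = **117 ml**, against about 120 ml stated under Potential Risks

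The post-meal tubes listed add to 5 + 6 = 11 ml rather than 13; with that figure the total is 117 − 2 × 2 = 113 ml. For PASC, month 12 adds 15 + 20 + 5 × 3.5 = 52.5 ml, giving 117 + 52.5 = 169.5 ml against about 175 ml.

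A further 20 ml laboratory set at month 1 would bring the mTBI total to 137 ml (133 ml by tube size), well above the stated figure. The volumes therefore agree with IGF-1 only. This excludes a second full set. It cannot exclude a glucose assay run on the same 3.5 ml, but no section lists one.

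**Step 2. Chemistry panels against drug exposure.**

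| Group | Drug | On-drug CMP | Drug time without a later on-drug CMP |
|---|---|---|---|
| mTBI | months 0–6 | month 6 ± 7 days, at completion | none left to cover |
| mTBI, re-injury extension | 6 further months | no draw listed in the extension | the whole extension |
| PASC | months 0–9 | month 6 ± 7 days | months 6–9: 3/9 = 33% |

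For mTBI, the time from the dose step to the first panel is 6 − 1 = 5 months, or 5/6 = 83% of treatment. For PASC, the first on-drug panel comes after 6/9 = 67% of treatment, and the next, at month 12, is 12 − 9 = 3 months after the last dose.

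**Step 3. Age of the PASC comparison.** On-file labs up to 6 months old, plus 6 months to the next panel, give a gap of up to about 6 + 6 = 12 months. No clinical panel is listed at month 0.

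**Step 4. Sections side by side.** Potential Risks and Adequacy of Protection Against Risks list raised glucose as a risk. Therapeutic Intervention reports no insulin resistance at this dose. The monitoring plan promises follow-up of laboratory values. The Blood draw section schedules no laboratory test between months 1 and 6, and none between months 6 and 12 for PASC. These sections do not show how the named risk is to be observed on drug.

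**The case against.** **The protocol gives a rationale.** It cites about 60 TBI research subjects over about 14 years, and about 100 clinic patients, treated at 0.6 mg/day, and calls the effects unlikely over a brief course. Experience at a dose and a list of potential risks are not strictly contradictory, and whether the experience suffices is a clinical judgement. That stands. But the research experience cited is in TBI, not PASC, and exposure here reaches 9 months for PASC and 6 + 6 = 12 months after re-injury.

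**Other safeguards exist.** Staff contact subjects monthly about adverse events, and vital signs, including weight, are taken at study visits. A symptomatic rise could therefore surface, and it would be wrong to infer that the risk cannot be detected at all. Nor is the dose step taken without any glucose information: a fasted CMP is scheduled at screening, though for PASC an older one may be substituted. What is missing is an on-drug value.

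**Stronger readings that the documents do not support.**

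- A reader might infer that nobody is charged with acting on month 6 or month 12 results, because the monitoring plan says "If screening reveals any clinical abnormalities, subjects will be advised". That item concerns potential subjects. The same plan makes the Principal Investigator responsible for safety, has data reviewed weekly, and grades laboratory alterations as adverse events.
- A reader might infer that the old PASC baseline is what prevents a month 6 change from being attributed to rhGH. There is no untreated PASC group, so a fresh baseline would not secure attribution either.
- A reader might infer that the promise to monitor laboratory values is broken. It names neither glucose nor a frequency, and some labs are drawn on drug.
- A reader might want a count of diabetic subjects at risk. The documents give no prevalence, and investigators may exclude at their discretion, so no count can be supported.

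**Conclusion.** The point holds as a gap in the schedule. Followed exactly, the plan gives no on-drug glucose before the month 1 dose step and none until mTBI treatment ends. PASC has no further blood in its last 3 months of drug, and the re-injury extension has no listed draw in 6 months. A rise without symptoms would go unseen during mTBI treatment; a symptomatic one might not.

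This rests on three assumptions: that the CMP includes glucose (its analytes are not listed); that the Blood draw section is complete; and that the unspecified metabolites measured at months 0 and 6 are not already reported to the team as a clinical glucose. If the third is wrong, a month 0 value exists, but the absence of an on-drug value before month 6 is unchanged.

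**What to change.** 1. Add a glucose assay to the existing month 1 safety draw, record whether the subject was fasting, and report the result to the study team with the IGF-1.
2. Report glucose from the fasted blood already drawn at month 0, so that every treated subject has a current pre-drug value whatever the age of the screening labs.
3. Reconcile Therapeutic Intervention and the Data Safety and Monitoring Plan with Potential Risks, Adequacy of Protection Against Risks and the laboratory schedule. The text should say what laboratory follow-up is intended for PASC months 6 to 9 and for the re-injury extension or, if none is, why.

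Any clinical response to a result is for the sponsor to set.

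The cost is one or two routine assays per treated subject and some redrafting, with no added visit. The documents do not say whether the existing tubes can yield a reportable glucose, so a small extra tube may be needed. Headroom under the stated totals is 120 − 117 = 3 ml for mTBI (7 ml by tube size) and 175 − 169.5 = 5.5 ml for PASC, so those totals may need updating. Fasting is not required at month 1, and a non-fasting value is harder to interpret, which is why fasting status should be recorded.
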